6.3.2.9. Presentation of Results

No formal inferential statistics (p-values) will be derived.

Continuous laboratory tests¹⁶ including glucose, cholesterol, triglycerides, low-density lipoprotein (LDL), high-density lipoprotein (HDL) and fasted glucose, will be summarized by means of descriptive statistics (including 90% CI of the mean change) by laboratory test, treatment group and analysis window. Actual values, changes from baseline and percent change from baseline will be tabulated separately. Continuous values for metabolic markers will be summarized in the pharmacodynamic analysis section.

Profile line plots by subject of all actual observed values using relative day (ADY) will be presented by treatment group. Graphs of the mean (+- SE) actual values over time and of the mean (+- SE) change from baseline, and percent changes from baseline will be presented for all continuous laboratory parameters, with the exception of the metabolic markers. Also, line plots for subjects will be provided by treatment group.

The analysis of abnormalities will focus on assessments reported during the treatment period. Results reported before baseline will only be listed.

Non-graded abnormalities and toxicities grades of the actual values will be presented as shift tables of the worst-case abnormality/toxicity grade versus the baseline abnormality/toxicity

¹⁶ With the exception of the metabolic markers [fasted insulin, homeostatic model assessment of insulin resistance (HOMA-IR) and HbA1c] and inflammation marker hsCRP.

grade. The table will be created per laboratory test, treatment group and analysis period. The results of non-graded abnormalities and toxicities grades will be shown separately.

A frequency table of the number (percent) of subjects with treatment-emergent worst-case abnormalities/toxicity grade per laboratory test, treatment group and analysis period will be presented. The results of non-graded abnormalities and toxicities grades will be shown separately.

A frequency table of the number (percent) of subjects will be also provided for hepatotoxicity flags defined before. These abnormalities will be also flagged in the individual data laboratory listing.

Listing will be provided for the laboratory test along with flag for abnormality results. In addition, pregnancy result will be listed separately.

6.3.3. Electrocardiogram

6.3.3.1. Available Data

The following ECG parameters will be analysed: heart rate (HR), RR interval, PR interval, QRS interval, uncorrected QT interval, QTcF (derived).

6.3.3.2. Derivation Rules

Derived Parameters

The Fridericia's cube-root corrected QT (QTcF) will be calculated using the following formula.

$$\text{Fridericia's cube-root corrected QT (Fridericia, 1920): } QTcF \text{ (ms)} = QT \text{ (ms)} \times \sqrt[3]{\frac{1000}{RR \text{ (ms)}}}$$

If RR is missing, then it will be derived from HR using the formula $RR(\text{ms}) = 60 \times HR(\text{bpm})$.

Handling of ECGs Measured in Triplicate

If ECG is collected in triplicates, the following approach will be taken.

First, any derivation of ECG parameters will be done before handling ECG triplicates. Next, the mean of the triplicate ECG values will be calculated for each individual ECG parameter, without rounding the result. These calculated means will constitute the analysis values; any derivation (e.g. change from baseline, assignment of abnormalities) and statistic will be based on the mean value of the triplicates.

The values of the original members of a triplicate will be listed.

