ICH	International Council for Harmonisation of Technical Requirements for Pharmaceuticals for Human Use
IEC	Independent Ethics Committee
IgG	immunoglobulin G
IL	interleukin
IP	investigational product
INR	international normalized ratio
IRB	Institutional Review Board
IXRS	interactive voice/web response system
JAK	Janus kinase
LDL	low-density lipoprotein
LFT	liver function test
LPS	lipopolysaccharide
LRV	lower reference value
MMRM	mixed models for repeated measures
mRNA	messenger ribonucleic acid
MTX	methotrexate

NOAEL	no-observed-adverse-effect level
NSAID	non-steroidal anti-inflammatory drug
P1NP	serum N terminal propeptide type I collagen
PBMC	peripheral blood mononuclear cells
█	███████████
PK	pharmacokinetic
pop-PK	population pharmacokinetics
q.d.	once daily
QTcF	QT interval corrected for the heart rate using Fridericia's formula
QTv	QT interval corrected by heart rate using the van de Water formula
RA	rheumatoid arthritis
SAE	serious adverse event
SAP	statistical analysis plan
SBP	systolic blood pressure
SD	standard deviation
█	███████████
SIK	salt-inducible kinase
SJC66	swollen joint count evaluated in 66 joints
SOC	System Organ Class
SUSAR	suspected unexpected serious adverse reaction
$t_{1/2}$	elimination half-life
TB	tuberculosis
TEAE	treatment-emergent adverse event
TJC68	tender joint count evaluated in 68 joints

TNF	tumor necrosis factor
TNFi	tumor necrosis factor inhibitor
TV	target value
ULN	upper limit of normal
VAS	visual analog scale
Vss	volume of distribution at steady state
WOCBP	women of childbearing potential

Definition of Terms

BMI body mass index

Weight (kg) / (height [m])²

QTcF QT interval corrected for heart rate using Fridericia's formula:

$$QTcF = QT/RR^{1/3}$$

RR = the interval from the onset of one QRS complex to the onset of the next QRS complex

DAS28 (CRP) disease activity score based on 28 joints

DAS28 (CRP) = 0.56 x $\sqrt{\text{TJC28}}$ + 0.28 x $\sqrt{\text{SJC28}}$ + 0.36 x $\text{Ln}[1+\text{CRP}(\text{in mg/L})]$ + 0.014 x patient's disease activity visual analog scale (VAS, in mm) + 0.96 (Mack, Hsia, & Aletaha, 2017)

TJC28 and SJC28 are the 28 joint counts for tenderness and swelling.

Ln = natural logarithm.

HOMA-IR Homeostatic model assessment of insulin resistance

HOMA-IR = (fasting insulin [mU/mL] x fasting glucose [mg/dL])/405

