8.5.4. Vital Signs

Vital signs (systolic and diastolic blood pressure taken at the same arm for each measurement, pulse and oral/tympanic body temperature, the same method of measuring body temperature to be used throughout the study) will be recorded in a standardized manner (i.e. after the subject has rested in a supine position for at least 5 minutes) at visits specified in the Schedule of Activities in Section 8.11 (see also Section 8.1, “Timing of Assessments”). Clinically significant abnormal values should be recorded as AEs.

8.5.5. 12-lead Electrocardiogram

At the time points specified in the Schedule of Activities (see Section 8.11 and also Section 8.1, “Timing of Assessments”), a triplicate 12-lead ECG will be recorded and results will be sent for central reading.

12-lead ECG recordings will be performed before blood sampling and after subjects rested for at least 5 minutes in supine position. In case an indwelling catheter is used, ECGs may be recorded after blood sampling, provided that there is at least 30 minutes between catheter insertion and the ECG recording. When catheter insertion would fail, the 12-lead ECG needs to be taken before the venipuncture and at least 30 minutes after the failed attempt. Triplicate ECGs will be performed within a time span of 10 minutes, with an approximate 3-minute interval between ECGs.

The following parameters need to be recorded: heart rate, RR interval, PR interval, QRS interval, uncorrected QT interval, morphology and rhythm analysis (QTcF will be derived). QTcF will be considered as normal if ≤ 450 ms (male) and ≤ 460 ms (female), while a prolongation of QTcF to > 500 ms or an increase from baseline > 60 ms will be considered a threshold of concern.

Immediately after recording, the ECG will be reviewed by the investigator on clinical significant abnormalities. This immediate review during the visit needs to be documented in the subject’s source. After receipt of the central report, also all flagged ECG abnormalities need to be assessed by the investigator on clinical relevance. Clinically significant abnormal findings should be recorded as AEs.

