4.3.4. Definition of Baseline

Baseline is defined as the last available assessment prior to the first intake of IP. For the parameters for which the time of assessment was planned to be collected, if for their assessment on the day of first intake the time is missing, their assessment at time point “PRE-DOSE” (when applicable) will be considered as baseline, otherwise, previous days last available assessment will be selected. For the parameters for which the time of assessment was not planned to be collected, their assessment on the day of first intake of IP will be considered as baseline. If multiple values on the same day qualify as last available assessment, the average of these values will be used in the analysis.

For ECG data assessed in triplicate, baseline is defined as the average (stored without rounding) of the combination of the most complete replicated ECG parameter before first intake of IP and at the same time the closest to it, selecting in the following order:

First consider Day 1, pre-dose:

- Select the average of the last available triplicate ECG parameter on that day;
- If there is no triplicate, select the average of the last available duplicate ECG parameter;
- In the absence of triplicates and duplicates the last available single ECG parameter will become baseline.

If baseline is not yet determined, consider the previous day and repeat the above selection (average of last triplicate, average of last duplicate, last single ECG on that day). Repeat the whole process successively for each previous day(s) as needed until baseline is determined.

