6.3.3.3. Abnormalities

The actual analysis values and changes from baseline of the QT and QTcF parameters will be categorized into the abnormality classes as defined in the SAP [Appendix II](#).

Worst-Case Abnormality

The worst-case post-baseline categorized actual analysis value and the worst-case categorized change from baseline for QT and QTcF will be determined per subject, per parameter, and for each analysis period, using all non-missing post-baseline records (including unscheduled and FU visits).

The worst-case categorized actual analysis value is the category corresponding to the highest post-baseline actual value. In case of several equal highest post-baseline actual values, the earliest occurrence will be taken for the analyses and will be flagged in the listings.

The worst-case change from baseline is the category corresponding to the largest increase (positive change) from baseline. In case of several equal largest increase from baseline, the earliest occurrence will be taken for the analyses and will be flagged in the listings.

Treatment-Emergent Abnormalities

Actual value: An abnormal post-baseline abnormality is defined as treatment-emergent when the abnormality is worse compared to the abnormality at baseline or when there is a change in direction (from H to L or from L to H). When the baseline value is missing, post-baseline abnormalities are considered as treatment-emergent.

An abnormal category for change from baseline is always treatment-emergent.

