Any laboratory parameter with treatment-emergent (i.e., worsening from baseline) abnormalities of grade 2 or above (ie, H2/L2 or higher/lower) should be considered a 'marked laboratory abnormality'. Marked laboratory abnormalities should be described in a corresponding section of the CSR as per ICH E3 guidance, section 12.4.2.3.

APPENDIX II: Vital Signs and Electrocardiogram grading**Table 4 Gradings for Vital Signs and Electrocardiogram Parameters**

Parameter	L1	L2	L3	L4	H1	H2	H3	H4
Systolic blood pressure (mmHg)	<90	<60	NA	NA	NA	≥140	≥160	≥180
Diastolic blood pressure (mmHg)	<60	<45	NA	NA	NA	≥90	≥100	≥120
Heart rate (bpm)	<60	<50	<40	NA	>100	>115	>130	NA
Body temperature (°C)	NA	<35	NA	NA	>38	NA	NA	NA
Respiratory rate (breaths per minute)	<12	NA	NA	NA	>20	NA	NA	NA
O ₂ saturation (%)	<95	<90	NA	NA	NA	NA	NA	NA
Weight	≥7% decrease from baseline	NA	NA	NA	≥7% increase from baseline	NA	NA	NA
QTc interval on ECG (ms)	NA	NA	NA	NA	>450	>480	>500	NA
QTc change from baseline (ms)	NA	NA	NA	NA	NA	>30	>60	NA
PR interval on ECG (ms)	<110	NA	NA	NA	>200	NA	NA	NA

Parameter	L1	L2	L3	L4	H1	H2	H3	H4
QRS complex on ECG (ms)	<60	NA	NA	NA	>120	NA	NA	NA

Source: FRM-MED-005/006, valid on 08JUL2020.

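### The SAP's fallback for a missing RR interval is inverted (60 × HR instead of 60,000/HR), so QTcF is understated by 26–54% at 50–100 bpm in any ECG replicate where it is used

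*SAP*

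**What the plan says.** SAP 6.3.3.2 calculates QTcF(ms) = QT(ms) × (1000/RR(ms))^(1/3). For gaps it adds: "If RR is missing, then it will be derived from HR using the formula" RR(ms) = 60 × HR(bpm). The Definition of Terms in the protocol gives "RR = the interval from the onset of one QRS complex to the onset of the next QRS complex".

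The same SAP section derives ECG parameters replicate by replicate and then averages the triplicate. It says of the averages: "These calculated means will constitute the analysis values". Under SAP 4.3.4 the baseline is likewise the average of the last available triplicate before first dose.

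These values are classified by SAP Appendix II, Table 4: QTc above 450 ms is H1, above 480 H2 and above 500 H3; a change from baseline above 30 ms is H2 and above 60 ms H3. SAP 6.3.3.3 takes the highest post-baseline value as the worst case and states: "An abnormal category for change from baseline is always treatment-emergent". SAP 6.3.3.4 tabulates worst-case shifts and treatment-emergent abnormalities.

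Protocol 8.5.5 requires both heart rate and RR to be recorded on each ECG, with central reading. It treats QTcF above 500 ms, or a rise above 60 ms, as a threshold of concern.

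**The concern.** The fallback makes RR lengthen as the heart beats faster, which contradicts the protocol's definition of RR. Because RR is in the denominator of the Fridericia correction, an RR that is too long gives a QTcF that is too short. The error can act in two directions:

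- **At a post-baseline visit** it lowers QTcF. It hides a prolongation if the affected visit was the subject's true worst one.
- **At baseline** it lowers the reference value. Every change measured at a later, unaffected visit then carries a false increase, and an abnormal change category always counts as treatment-emergent.

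With 15 and 10 subjects planned, one misclassified subject moves a frequency by 1/15 = 6.7 or 1/10 = 10 percentage points. RR is also an analysed parameter under SAP 6.3.3.1, so its own summaries would be distorted.

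**Working it through.** The plan states no figure to reproduce here; the check is algebra on the printed formulas.

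**Main formula.** The protocol's QT/RR^(1/3), with RR in seconds, and the SAP's QT × (1000/RR)^(1/3), with RR in ms, agree: QT 400 ms with RR 857 ms gives 421.1 ms both ways. Only the fallback is wrong.

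**Fallback.** A minute is 60,000 ms, so RR(ms) = 60,000/HR. Reading the multiplication sign as a division does not help: 60/HR gives seconds, while the SAP states ms.

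**Effect on one replicate.** The ratio of SAP to correct QTcF is

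f = [(60,000/HR)/(60 × HR)]^(1/3) = (1000/HR²)^(1/3)

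With one of three replicates affected, the triplicate mean is low by (1 − f)/3.

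| HR (bpm) | RR by SAP (ms) | Correct RR (ms) | f | Replicate QTcF low by | Triplicate mean low by, one replicate affected |
|---|---|---|---|---|---|
| 50 | 3000 | 1200 | 0.7368 | 26.3% | 8.8% |
| 60 | 3600 | 1000 | 0.6525 | 34.8% | 11.6% |
| 75 | 4500 | 800 | 0.5623 | 43.8% | 14.6% |
| 100 | 6000 | 600 | 0.4642 | 53.6% | 17.9% |

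The error vanishes at 31.6 bpm and reverses below that, outside the range considered.

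**Effect on the analysed value.** With k of three replicates affected and the same HR in all three, the mean is true QTcF × [1 − k(1 − f)/3]. The true values below are illustrative assumptions.

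*Masked level.* True QTcF 510 ms (H3) at 60 bpm:
- k = 1: 450.9 ms (H1)
- k = 2: 391.8 ms (no grade)
- k = 3: 332.8 ms (no grade)

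At 75 bpm, k = 1 gives 435.6 ms (no grade).

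*False rise.* True QTcF is 400 ms throughout and only the baseline is affected. The false change is 400 × k(1 − f)/3. At 60 bpm:
- k = 1: +46.3 ms (H2)
- k = 2: +92.7 ms (H3)
- k = 3: +139.0 ms (H3)

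For k = 1 at other rates it is +35.1 ms at 50 bpm, +58.4 at 75 and +71.4 at 100.

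*Rate at which one affected baseline replicate crosses a cut-off T.* Solving 400(1 − f)/3 = T gives HR = √[1000/(1 − 3T/400)³]. For T = 30 this is √(1000/0.775³) = 46.3 bpm; for T = 60 it is √(1000/0.55³) = 77.5 bpm.

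*Masked rise.* A true rise from 400 to 470 ms at 60 bpm (+70, H3), with one post-baseline replicate affected: 470 × (1 − 0.3475/3) = 415.6 ms, so the change shows as +15.6 ms (no grade).

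**The case against.** The strongest reply is that the rule may never be used. RR is a required parameter, recordings are centrally read, and nothing in the documents suggests that RR will be missing. This stands: the expected effect cannot be estimated and may be zero.

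Second, the 26–54% applies to a replicate, while the analysed quantity is the triplicate mean. This also stands, and the diluted figures are the relevant ones when only one replicate is affected.

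Third, the false rise needs an unaffected later visit. If RR were missing in the same way at both visits, much of the error would cancel. At 60 bpm with one replicate affected each time, a stable 400 ms shows no change and a true +70 ms shows 70 × 0.8842 = +61.9 ms, still H3. With all three affected each time it shows 70 × 0.6525 = +45.7 ms, now H2. So cancellation removes the false rise at a stable heart rate, but not all of the masking.

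Fourth, the error would be conspicuous. RR values of 3600–6000 ms would appear in summaries and subject plots, and the individual replicates are listed. That makes discovery likely but does not make the rule correct.

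Finally, the ECG tables are descriptive. Site review, central reading and uncorrected QT do not depend on the formula, and the separate derivation document that the SAP mentions may carry the right rule. All of this limits the consequences; none of it supports the formula as printed.

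**Conclusion.** The concern holds. The fallback is wrong as written, and no choice of units rescues it. Wherever it is used at 50–100 bpm it understates QTcF by 26–54% in the replicate, and by 9–18% in the triplicate mean if one replicate is affected. That is enough to move a subject across the SAP's own QTc categories in either direction.

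The size rests on three assumptions: an illustrative heart-rate range, because the documents give no distribution; equal heart rate across the three replicates; and the true QTcF values chosen for the examples. The practical effect depends on how often RR is missing while HR is present, and is nil if that never happens. Certainty is high about the formula and not about any effect on results. The primary endpoint is not affected. This should be fixed: a definite error in a safety derivation, with conditional impact and negligible cost to correct.

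**What to change.** Replace the fallback in SAP 6.3.3.2 with RR(ms) = 60,000/HR(bpm), after confirming the printed formula on the original page. Check the analysis program and the separate derivation document against the corrected rule. Flag every record with a derived RR in the ECG listing and report how many there are, by treatment group and by baseline or post-baseline visit. If the count is zero, say so, and the matter is closed.

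The cost is one line in the SAP, a program check and a listing flag. Data collection does not change.

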6.3.3.3. Abnormalities

The actual analysis values and changes from baseline of the QT and QTcF parameters will be categorized into the abnormality classes as defined in the SAP [Appendix II](#).

Worst-Case Abnormality

The worst-case post-baseline categorized actual analysis value and the worst-case categorized change from baseline for QT and QTcF will be determined per subject, per parameter, and for each analysis period, using all non-missing post-baseline records (including unscheduled and FU visits).

The worst-case categorized actual analysis value is the category corresponding to the highest post-baseline actual value. In case of several equal highest post-baseline actual values, the earliest occurrence will be taken for the analyses and will be flagged in the listings.

The worst-case change from baseline is the category corresponding to the largest increase (positive change) from baseline. In case of several equal largest increase from baseline, the earliest occurrence will be taken for the analyses and will be flagged in the listings.

Treatment-Emergent Abnormalities

Actual value: An abnormal post-baseline abnormality is defined as treatment-emergent when the abnormality is worse compared to the abnormality at baseline or when there is a change in direction (from H to L or from L to H). When the baseline value is missing, post-baseline abnormalities are considered as treatment-emergent.

An abnormal category for change from baseline is always treatment-emergent.

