9.3.5.5. Vital Signs

Vital signs will be analyzed descriptively. Changes from baseline will be presented as well. Analyses will be done per treatment group.

9.3.5.6. 12-Lead Electrocardiogram

A descriptive analysis will be done for the 12-lead ECG. Changes from baseline (Day 1 predose) will be presented as well. Frequency analyses of abnormalities based on actual values and on changes from baseline will be presented as well. Analyses will be done per treatment group.

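### SAP 6.3.3.3 categorizes only QT and QTcF, so the Appendix II limits for PR, QRS and heart rate feed no shift or treatment-emergent table in the ECG section

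*SAP*

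**What the plan says.** SAP 6.3.3.1 lists six ECG parameters for analysis: heart rate, RR, PR, QRS, uncorrected QT and QTcF. SAP 6.3.3.3 then restricts classification to two of them: "The actual analysis values and changes from baseline of the QT and QTcF parameters will be categorized into the abnormality classes" of Appendix II. The worst-case rule has the same restriction: "the worst-case categorized change from baseline for QT and QTcF will be determined per subject, per parameter, and for each analysis period". For actual values, the worst case is the class of the highest post-baseline value.

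The treatment-emergent rule in 6.3.3.3 counts an abnormality that is worse than at baseline, or one that has switched between the high and the low class. SAP 6.3.3.4 presents worst-case abnormalities in shift tables and in a treatment-emergent frequency table.

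Appendix II, Table 4, covers vital signs and ECG together. It has rows for heart rate, QTc, QTc change from baseline, PR and QRS, and none for uncorrected QT.

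Protocol 9.3.5.6 (12-Lead Electrocardiogram) is not limited to QT: "Frequency analyses of abnormalities based on actual values and on changes from baseline will be presented as well". Protocol section 9 requires departures from the protocol to be justified in the SAP. SAP 6.7 answers that no changes apply.

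**The concern.** The classification rule and the table of limits do not match. Section 6.3.3.3 sends uncorrected QT to an appendix that has no limits for it. It leaves out PR and QRS, which are recorded, analysed and given limits. A programmer cannot carry out the QT part and has no instruction to apply the PR and QRS limits.

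What is at stake is the count, by arm, of subjects who newly cross the sponsor's own PR, QRS and ECG heart-rate limits. The protocol treats conduction as relevant to safety: exclusion criterion 17 and the treatment discontinuation conditions in section 6.4 both name conduction abnormality and not only QTcF. With 15 and 10 subjects planned, counts of individual threshold crossings are more informative than a comparison of arm means.

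**Working it through.** The plan gives no figure to reproduce, so the check sets the sections side by side.

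| Parameter (SAP 6.3.3.1) | Appendix II limits, actual value | Appendix II limits, change | Categorized by 6.3.3.3? |
|---|---|---|---|
| QTcF (QTc rows) | >450, >480, >500 ms | >30, >60 ms | Yes |
| Uncorrected QT | none | none | Yes, but nothing to apply |
| PR | <110; >200 ms | none | No |
| QRS | <60; >120 ms | none | No |
| Heart rate | <60, <50, <40; >100, >115, >130 bpm | none | No |
| RR | none | none | No |

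**Step 1, rows used.** Table 4 has five ECG-relevant rows: heart rate, QTc, QTc change, PR and QRS. Section 6.3.3.3 can use the two QTc rows. That leaves 5 − 2 = 3 rows. No other SAP text applies the PR and QRS rows. The heart-rate row may be used elsewhere, because SAP 6.3.4.3 classifies vital signs by Appendix II, 6.3.4.1 includes pulse rate among them, and the appendix has no separate pulse row.

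**Step 2, effect on tables.** The shift and treatment-emergent tables in 6.3.3.4 need a class for each value. Only QT and QTcF are assigned classes, and QT has no limits. As written, the tables can therefore be filled for QTcF alone.

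**Step 3, the direction clause.** A switch between high and low needs a parameter with classes on both sides. The QTc rows have no low class, so the clause cannot operate on them. PR, QRS and heart rate each have both. This is consistent with a drafting gap, but the documents do not state the intent.

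**Step 4, the worst-case rule.** The rule takes the highest value. For QTcF that is enough, because only high classes exist. For PR, a subject with one value below 110 ms and another between 110 and 200 ms would be classed by the second value, as normal. Adding PR, QRS and heart rate without changing this rule would miss low values.

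**Step 5, against the protocol.** Protocol 9.3.5.6 plans abnormality frequencies for the 12-lead ECG without naming parameters. The SAP restricts threshold-based frequencies to QT and QTcF, and 6.7 does not record that.

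**The case against.** A reader might infer that conduction abnormalities are never tabulated, or that one abnormal subject would be hidden in an arm mean. Suppose PR rises from 160 to 230 ms in one of 15 subjects. The arm mean then moves by (230 − 160)/15 = 4.7 ms, which is easily overlooked. The documents do not support the inference:

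- SAP 4.4.2 includes minimum and maximum, and 6.3.3.4 summarizes both actual values and changes. If the value falls in an analysis visit, the table shows a maximum of at least 230 ms and a maximum change of at least 70 ms.
- SAP 6.3.3.4 also plans subject-level plots of observed values and of change from baseline, a listing, and a frequency table of CRF ECG interpretations by arm and time point.
- Protocol 8.5.5 requires clinically significant ECG findings to be recorded as AEs. Those that are treatment-emergent enter the TEAE tables.

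Other arguments have some force. Heart rate is not a conduction interval, and its row may be meant for pulse rate. A row in Table 4 does not prove intended use, since the table also lists respiratory rate and oxygen saturation, which are not among the vital signs in SAP 6.3.4.1. Protocol 9.3.5.6 names no parameters and Protocol 8.5.5 gives numeric thresholds only for QTcF, so QTcF categories plus the CRF table could be argued to satisfy it. The direction clause is merely idle for QTc and changes no QTc result.

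These arguments limit the point but do not remove it. CRF interpretation and AE recording depend on investigator judgement, and the documents do not show whether the CRF categories separate conduction findings. Extremes and plots give neither a shift from baseline nor a treatment-emergent count. Unlike respiratory rate and oxygen saturation, PR and QRS are collected and analysed in this study.

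**Conclusion.** The point holds as a gap in threshold-based tabulation, not as a loss of ECG data. It is firm for PR and QRS, and weaker for heart rate because of the pulse-rate route. Uncorrected QT is a separate, smaller defect: it is named for classification without limits. The narrowing relative to Protocol 9.3.5.6 should at least be declared.

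The practical size is modest. The affected tables are descriptive safety outputs in a study of 25 planned subjects, and neither the primary endpoint nor any inferential result is touched. The correction is still worthwhile, because it adds safety counts from data and limits that already exist.

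This rests on three assumptions: that the tables in 6.3.3.4 take their classes from 6.3.3.3; that the QTc rows are meant for QTcF, the only corrected QT analysed; and that the separate document with derivations and mock tables, mentioned in SAP section 1 and not available here, does not already extend the classification.

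**What to change.** Amend SAP 6.3.3.3 as follows:

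- Categorize actual values of QTcF, PR, QRS and ECG heart rate by the Appendix II limits.
- Keep change-from-baseline classes for QTcF only. Among the ECG parameters, Appendix II gives change limits only for QTc, so extending them to PR, QRS or heart rate would again name parameters that have no limits.
- Drop uncorrected QT from the categorization, or add limits for it to Appendix II.
- For actual values, determine the worst case separately for the low direction (lowest value) and the high direction (highest value). A subject with both is counted once in each, as SAP 6.3.2.7 already does for non-graded laboratory abnormalities.
- State whether the heart-rate row applies to ECG heart rate, to pulse rate under vital signs, or to both.

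Then add PR, QRS and ECG heart rate to the existing shift and treatment-emergent tables in 6.3.3.4. If the sponsor prefers the narrower scope, SAP 6.7 should say that the PR and QRS rows are not used and justify the departure from Protocol 9.3.5.6.

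The cost is SAP wording and a few extra table rows. No new data, visits or limits are needed, unless limits for uncorrected QT are added.
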